5.8. Safety Analyses

5.8.1. Adverse Events

Verbatim descriptions of AEs will be coded using Version 20.0 of MedDRA. Summary tables will be provided for all treatment-emergent AEs (TEAEs). A TEAE is defined as any AE that newly appeared, increased in frequency, or worsened in severity following initiation of study drug. An AE is considered treatment emergent if the AE starts on or after the first dose of study drug. In addition, all AEs (including non-TEAEs), serious TEAEs, and TEAEs leading to study drug discontinuation will be provided in listings by treatment group, site, subject, verbatim term, MedDRA SOC and preferred term, start and end date, seriousness flag, severity, relationship to study drug, action taken with study treatment, frequency and outcome. All AEs will be coded using the MedDRA coding system and displayed in tables and data listings using SOC and preferred term.

An overall summary of AEs will include number and percentage of subjects in each treatment group who experienced at least 1 AE of the following categories: any AE, any TEAE, any drug-related TEAE (defined as possibly, probably or definitely related to study drug), any severe TEAE, any serious TEAE (SAE), any drug-related SAE, any SAE leading to death, any TEAE leading to premature discontinuation of study drug, and any SAE leading to premature study drug discontinuation.

The number and percentage of subjects reporting a TEAE in each treatment group will be tabulated by SOC and preferred term; by SOC, preferred term, and severity (mild, moderate,

and severe); and by SOC, preferred term, and relationship (unrelated [defined as unrelated or unlikely related to study drug] or related to study drug). The number and percentage of subjects reporting a SAE and reporting a TEAE leading to premature discontinuation of study drug in each treatment group will also be summarized by SOC and preferred term. Summary tables will be presented alphabetically by SOC and preferred term within SOC. The incidence of TEAEs that occur in at least 2% of subjects in either treatment group will be summarized by preferred term and treatment group, sorted by decreasing frequency in the eravacycline group. For all analyses of TEAEs, if the same AE (based on preferred term) is reported for the same subject more than once, the AE is counted only once for that preferred term and at the highest severity and strongest relationship to study drug. Events with missing severity will be considered severe and events with missing relationship to study drug will be considered related to study drug.

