Aerobic and anaerobic blood cultures will be obtained at two separate sterile venipuncture sites prior to initiation of study drug therapy. Upon knowledge of a positive culture for a pathogen, blood cultures should be repeated until sterile (i.e., both sets of cultures from two separate venipuncture sites are negative for pathogens) through the FU visit. If baseline cultures are negative, follow-up cultures should be obtained only if clinically indicated (e.g., signs and symptoms of persistence, relapse, or new infection).

Each subject will receive 7-10 doses of study drug (total IV and PO). Visits will be conducted at Day 5, EOI and EOT; the TOC visit will be 14-17 days after randomization, and at least 5 days after the last dose of study drug; the FU visit will take place 21-28 days after randomization. At any time, the Investigator may discontinue the subject from study drug based on the best interests of the subject. Prior to starting non-study antibiotics, the EOT assessments must be performed. The subject should remain in the study and all applicable procedures should be followed through FU.

Table 2: Timeline for Individual Study Subjects

Screening	Randomization	Study Drug Treatment	Day 5 Visit	End of IV (EOI) Visit	End of Treatment (EOT) Visit	Test of Cure (TOC) Visit	Follow-up (FU) Visit
Within 36-h prior to Randomization		Dose Cycles 1-10	5 days after Randomization	Within 1 day of Last IV Dose	Within 1 day of Last Dose (IV or PO)	14-17 days after Randomization & ≥ 5days after Last Dose	21-28 days after Randomization

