13.1 Definitions

13.1.1 Adverse Event

An adverse event is any adverse experience in a subject administered a pharmaceutical product, whether or not it is considered drug-related, that occurs during a subject's study participation (defined as after the time of initial informed consent). This would include any side effect, injury, toxicity, sensitivity reaction, or intercurrent illness. A pre-existing condition is one that is present at study entry and is reported as part of the subject's medical history. It should be reported as an AE if the frequency, intensity, or character of the condition worsens during study drug treatment. Subjects should be instructed to report all AEs to the Investigator or study staff. Adverse events must be appropriately documented in the subject's original source documents and entered into the eCRF. Investigators should report syndromes rather than list symptoms.

Events that result from lack of efficacy of study drug (eg, treatment failure) are not considered AEs.

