1.1.2. Study Objectives

The primary objective is to demonstrate that IV eravacycline is non-inferior to ertapenem in responder outcome (clinical cure and microbiologic success) in the micro-ITT population at the EOI visit (within 1 day of the completion of IV study drug treatment) and TOC visit (defined as 14-17 days after randomization).

The secondary objectives of the study are:

- To compare responder outcomes in the treatment arms at Day 5 in the micro-ITT population
- To compare clinical outcomes in the treatment arms at Day 5, EOI, End of Treatment (EOT), TOC, and Follow-up (FU) visits in the following populations:
 - ITT population
 - Clinically evaluable (CE) population
 - Micro-ITT population
 - Micro-MITT population
 - ME population
- To compare microbiologic outcomes in the treatment arms at Day 5, EOI, EOT, TOC and FU visits in the following populations:
 - Micro-ITT population
 - Micro-MITT population
 - ME population
- To assess safety and tolerability of IV eravacycline administration in the safety population
- To explore PK parameters of IV eravacycline

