11. If a local serum pregnancy test is not available or results cannot be received within 4 hours of sampling at the investigative site then a urine pregnancy test may be utilized locally to obtain timely results for randomization. All female subjects of childbearing potential will have a serum pregnancy test performed by the central laboratory.
12. Obtain a set of aerobic and a set of anaerobic samples from 2 separate venipuncture locations at Screening. Upon knowledge of a positive culture for a pathogen, blood cultures should be repeated until sterile (ie, both sets of cultures from 2 separate venipuncture sites are negative for pathogens) through the FU visit. Await results before drawing additional sets of blood cultures. If baseline cultures are negative, follow-up cultures should be obtained only if clinically indicated (eg, signs and symptoms of persistence, relapse, or new infection).
13. Collected from a mid-stream urine specimen, a newly-placed urinary catheter, cystoscopy, suprapubic aspiration, or a properly disinfected collection port.
Urine cultures should be processed using a calibrated loop to identify a quantitative count of bacteria at a lower limit of 103 CFU/mL. The colony count and pathogenic microorganism(s) identification will be recorded and the purified isolate(s) will be sent to the central laboratory where species confirmation and antimicrobial susceptibility testing will be performed.
14. Document any adverse events that occur from the signing of informed consent through study completion. Prior conditions should be documented as medical history
15. Expected treatment duration is 7 days unless clinical failure occurs earlier; maximum treatment duration is ten days (total IV and PO). The 24-h interval between IV doses can be shortened (but not prolonged) by up to 2-h (ie, interval of 22-h to 24-h) from the first dose during doses 1-3 to adapt to a normal hospital schedule. After the third dose, the permitted IV administration window is q24h ± 90 minutes. At a minimum, the first 5 IV doses must be administered in an in-patient hospital setting; subsequent doses may be administered on an out-patient basis. Contact Medical Monitor for dosing beyond 7 doses.
16. Subjects should receive 7-10 days of treatment. Specific criteria for determining length of treatment are described in Protocol Section 11.3.3.
17. Please refer to Protocol Section 24 for schedule of plasma PK sample collection on Day 1, Day 2, and Day 5.

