4.6. Missing, Unused, and Spurious Data

Missing data will be handled as outlined below:

- All missing and partial dates for events occurring after randomization or for medications received after randomization will be queried for a value. If no value can be obtained, substitutions will be made as follows:
 - For date of cUTI diagnosis, if the day is missing, day will be defined as “01.” If the month and day are missing, no imputation will be made. For start dates, missing months and days will be defined by “01,” as long as this occurs on or after the first dose of study drug. If the algorithm produces a date prior to the first dose of study drug, the date of the first dose of study drug will be used for the partial date. For stop dates, missing months will be defined as “12” and days will be defined by the last day of the respective month. If the algorithm produces a date after the study discontinuation/completion date, the date of study discontinuation/completion will be used for the partial date. These substitutions will be used in calculations; however, the actual value recorded on the eCRF will be used for all listings.
 - Missing times for AEs will be queried for a value. If no value can be obtained and for all other times for events and assessments occurring after randomization, the time will not be imputed but will remain missing.
- The severity and causality assessment for AEs should not be missing and will be queried for a value. Should there be missing data, AEs with missing severity will be considered severe and AEs with missing relationship to study drug will be considered related to study drug.
- For clinical and microbiological response, missing data will be handled as follows:
 - For the outcome measure of clinical response:
 - Subjects will be defined as an indeterminate if the Investigator cannot determine whether the subject is a clinical cure or failure. Outcome will be defined as missing if the Investigator did not complete the assessment,

or if the subject did not complete the study visit. For the purposes of analysis missing data will be considered indeterminate, and by definition, subjects with an indeterminate response are included in the denominator for analyses in the ITT, micro-ITT and micro-MITT analysis sets, and thus, are considered failures. Subjects with an indeterminate response are excluded from the CE and ME populations.

- For outcome measure of microbiologic response:

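### The SAP's start-date rule for treatment-emergent AEs is narrower than its own definition and should gain a worsening limb

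*SAP*

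**What the plan says.** SAP section 5.8.1 makes two consecutive statements about treatment emergence.

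- The definition: "A TEAE is defined as any AE that newly appeared, increased in frequency, or worsened in severity following initiation of study drug". Protocol section 15.2.2 gives the same definition and nothing narrower.
- The working rule that follows it: "An AE is considered treatment emergent if the AE starts on or after the first dose of study drug".

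Three other provisions decide which events can fall between the two.

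- AE collection begins before dosing. SAP section 1.2.3 (schedule footnote 14) says: "Document any adverse events that occur from the signing of informed consent through study completion". The same footnote sends prior conditions to medical history.
- The screening column of Table 2 in the protocol summary reads "Within 36-h prior to Randomization".
- Protocol section 13.1.1 says of a pre-existing condition: "It should be reported as an AE if the frequency, intensity, or character of the condition worsens during study drug treatment".

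Events that are not treatment emergent are still shown. Section 5.8.1 says that "all AEs (including non-TEAEs), serious TEAEs, and TEAEs leading to study drug discontinuation will be provided in listings", and the overall AE summary has a row for any AE.

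**The concern.** The definition has three limbs: new onset, increased frequency and worsened severity. The rule has one, the start date. A programmer needs only two dates to apply the rule, whereas the definition gives no algorithm for detecting worsening. The rule is therefore the likelier of the two to be coded. SAP section 6 records no intended departure from the protocol, so the narrowing looks inadvertent.

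The TEAE flag drives most of the AE output in section 5.8.1: the system organ class and preferred term tables, the breakdowns by severity and relationship, and the rows for severe TEAEs, serious TEAEs and TEAEs leading to discontinuation. Suppose an AE is mild when it arises after consent, then becomes severe on drug and ends treatment. By the SAP's own definition it belongs in those tables. If the flag looks only at the original start date, it is in none of them.

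Pre-dose onset should be balanced between arms by randomization. Worsening on drug need not be, so any loss could fall more heavily on the arm with more worsening.

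**Working it through.** Neither document gives a figure to reproduce. The check is to pass each kind of event through both statements.

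| Event | Definition | Start-date rule |
|---|---|---|
| 1. Symptom present at entry, no worsening | Not an AE (medical history) | Not an AE |
| 2. Pre-existing condition that worsens on drug | TEAE | TEAE, if onset is dated at the worsening |
| 3. AE first arising after the first dose | TEAE | TEAE |
| 4. AE arising between consent and first dose, no worsening | Not a TEAE | Not a TEAE |
| 5. As 4, worsens on drug, new record at the worsening | TEAE | TEAE |
| 6. As 4, worsens on drug, original record and start date kept | TEAE | **Not a TEAE** |

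The statements clearly disagree only in row 6. Row 2 rests on a presumption: Protocol section 13.1.1 requires the AE to be reported but does not say which onset date to enter. Rows 5 and 6 differ only in how worsening is recorded, and neither document states that convention.

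**How long the gap can be.** The relevant interval runs from consent to first dose. Its upper limit is the 36-hour screening window plus the time from randomization to first dose, which is not stated. Taking that time as zero, with follow-up ending 21 to 28 days after randomization:

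- 1.5 / (1.5 + 21) = 1.5 / 22.5 = 6.7% of the screening-to-follow-up period
- 1.5 / (1.5 + 28) = 1.5 / 29.5 = 5.1%

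Apart from the unstated dosing delay, these are ceilings. Standard-of-care screening work may precede consent, and Dose 1 may fall on the screening day (Protocol sections 3 and 11.2.1), so the interval can be a few hours.

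**Partial dates.** SAP section 4.6 covers incomplete start dates for events after randomization: "If the algorithm produces a date prior to the first dose of study drug", the first-dose date is substituted. Such events are therefore counted as TEAEs, which narrows the gap a little further.

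**What remains visible.** A row 6 event stays in the all-AE listing, with its dates and severity, and in the any-AE row. It is lost from the TEAE tabulations, not from the report.

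**The case against.** The strongest defence is that nothing is necessarily lost. The second sentence says *if*, not *only if*, and it follows directly after a definition that includes worsening. A careful programmer could treat onset after dosing as sufficient and worsening as a second route. This stands as a reading, but the SAP gives no algorithm for that second route, so the text should not depend on it.

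A reader might infer that the rule loses the events of most interest, because nausea and vomiting are both entry symptoms and known effects of the drug. The documents do not support that. Symptoms already present at entry are medical history, and if they worsen on treatment they are reported as AEs, presumably with onset after the first dose. Nor do the earlier trials point one way. Nausea was 18.0% against 3.1% in the previous cUTI trial, but that regimen included oral eravacycline and the comparator was levofloxacin. At 1.5 mg/kg q24h against ertapenem, the phase 2 cIAI trial had nausea of 1.9% against 6.7% and emesis of 5.7% against 0%.

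A reader might also infer that, because the rule has no end date, it wrongly pools events from the shared levofloxacin phase into a comparison whose objective is "To assess safety and tolerability of IV eravacycline administration in the safety population". That is a separate matter and contradicts nothing:

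- The randomized arms are IV-to-oral regimens, and a by-arm tabulation over the full course compares them validly.
- A shared oral-phase rate barely moves the risk difference. As an illustration, take IV-phase nausea of 8.1% and 0.7% (the phase 3 cIAI trial, at a different eravacycline regimen) and an assumed independent oral-phase rate of 3.1% in both arms. Then 1 − 0.919 × 0.969 = 11.0% and 1 − 0.993 × 0.969 = 3.8%. The difference goes from 7.4 to 7.2 points. The risk ratio does fall, from 11.6 to 2.9, but the SAP plans counts and percentages, not ratios.
- A cut at the first oral dose has its own problems. That dose comes about 24 hours after the last infusion starts, and the reported half-life is 29.34 hours. Under simple one-phase decay, 2^(−24/29.34) = 57% of the drug would remain. The switch also requires adequate appetite and clinical improvement (Protocol section 11.3.2), so the cut-off is itself a post-randomization outcome that nausea could affect.

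**Conclusion.** The inconsistency is real and minor. SAP section 5.8.1 states a definition with worsening and frequency limbs, then a rule without them. The rule misclassifies an event only if two conditions both hold: it is applied as the sole test, and worsening keeps the original record and start date. The documents settle neither. The events exposed are those that are new after consent, begin before the first dose and then worsen on drug. Their number cannot be derived from the documents and is probably small.

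Nothing here shows that the planned safety comparison is biased or that the oral phase is handled wrongly. The case for a change is that the main AE tables should follow the SAP's own definition, and at present the text leaves that to the programmer.

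**What to change.** 1. Extend the rule in SAP section 5.8.1: *An AE is treatment emergent if it starts, or increases in frequency or severity, on or after the first dose of study drug.*
2. State in the SAP and the eCRF completion instructions that worsening of a pre-dose AE is entered as a new record dated at the worsening. This convention matters as much as the wording: if a single record holds one start date and one severity, the data do not show when the worsening occurred and no rule can recover it.
3. If data are already being collected, list, without treatment codes, the AEs that start before and continue past the first dose, and query whether any worsened. This gives the actual number affected before database lock.

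The cost is one sentence, one data-entry convention and a short blinded listing. No planned table is lost. A table of TEAEs with onset during the IV phase could be added for description, with the carry-over and switch-timing limits noted, but it is optional and is not part of this correction.

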5.8.2. Laboratory Data

Summaries of central laboratory data will include hematology (erythrocyte count [RBC], hematocrit, hemoglobin, mean cell hemoglobin [MCH], mean cell hemoglobin concentration [MCHC], mean cell volume [MCV], leukocyte count [WBC], absolute and differential basophils, absolute and differential eosinophils, absolute and differential lymphocytes, absolute and differential monocytes, absolute and differential neutrophils, and absolute and differential platelets), chemistry (tests included in [Table 6](#)), coagulation (fibrinogen, partial thromboplastin time, and prothrombin time), and urinalysis (bilirubin, casts, crystals, glucose, ketones, pH, protein, RBC, urobilinogen, and WBC) laboratory parameters. Laboratory parameters will be presented in alphabetic order with the following exceptions: differentials of WBC counts will be presented following the WBC results, and chemistry parameters will first be grouped by organ class (renal, liver, electrolytes and other) and presented alphabetically within each of these classes, as shown in [Table 6](#). Clinical laboratory values will be expressed in System International (SI) units. Box plots showing the minimum, maximum, and quartile values will be presented for all visits by treatment group.

Table 6 Presentation of Chemistry Parameters

Renal	Blood urea nitrogen Creatinine
Liver	Alkaline phosphatase ALT AST Bilirubin indirect Bilirubin total GGT LDH
Electrolytes	Bicarbonate Calcium Chloride Magnesium Potassium Sodium
Other	Albumin Amylase

	Cholesterol (total) Creatine kinase Glucose, non-fasting Lipase Phosphorus Total protein Uric acid
--	--

Key: ALT = Alanine Aminotransferase; AST = Aspartate Aminotransferase; GGT = Gamma-Glutamyl Transferase; LDH = Lactate Dehydrogenase.

Baseline is defined as the value closest to but prior to the start of study drug administration. Analyses will utilize assessments occurring during safety analysis windows (see [Table 2](#)). Thus, if a subject has a visit outside the window, for example, a TOC visit on Day 11, the laboratory assessment will not be summarized with the TOC visit but will be considered an unscheduled assessment. If more than 1 measurement is taken during the visit window, the value taken on the scheduled visit will be utilized or if no scheduled visit was done, the first (earliest) measurement will be used. If more than 1 measurement is taken on the same day, the last measurement on the day will be used. For worst overall post-baseline analyses, all laboratory assessments including those obtained from unscheduled visits will be included.

Several analyses of the laboratory data will be presented. Descriptive statistics (based on SI units) for chemistry, hematology and coagulation values and the change from baseline will be summarized by treatment group at Day 5, EOI, EOT, TOC and FU visits, and for the overall worst value post-baseline (which includes unscheduled visits). Change from baseline will be calculated for each patient at the specified time point as the value at the specified time point minus the baseline value.

Toxicity grade will be determined based on the modified Division of Microbiology and Infectious Diseases (DMID) criteria in [Table 7](#). The DMID Adult Toxicity Table (November 21, 2007) was modified to exclude the clinical component of the toxicity grading. In addition, Grade 0 was added to the table so that shifts from normal could be analyzed. For toxicity grades based on a multiple of the ULN, the normal range from the central laboratory will be applied. For toxicity grades based on fixed values, the grades will be assigned regardless of the normal actual range values from the central laboratory. For example, a hemoglobin value of 10.0 gm/dL will be assigned a grade of 1 toxicity, even if the lower limit of normal from the laboratory was 9.8 gm/dL. Shift tables will be presented to show the number of subjects with a laboratory value with a grade of 0, 1, 2, 3 or 4 at baseline versus the worst post-baseline value.

Table 7 Modified Division of Microbiology and Infectious Diseases Adult Toxicity Criteria (November, 2007)

Hematology					
	Grade 0	Grade 1	Grade 2	Grade 3	Grade 4
Hemoglobin (gm/dL)	>10.5	9.5-10.5	8.0-9.4	6.5-7.9	<6.5
Absolute Neutrophil Count (count/mm ³)	>1,500	1,000-1,500	750-999	500-749	<500
Platelets (counts/mm ³)	≥100,000	75,000-99,999	50,000-74,999	20,000-49,999	<20,000
WBC (count/mm ³)	1,000-10,999	11,000-12,999	13,000-14,999	15,000-30,000	>30,000

% Polymorphonuclear Leucocytes	≤80%	>80%-90%	>90-95%	>95%	--
--------------------------------	------	----------	---------	------	----

Key: WBC = White Blood Cell Count.

Chemistry					
	Grade 0	Grade 1	Grade 2	Grade 3	Grade 4
Hyponatremia (mEq/L)	>135	130-135	123-129	116-122	<116
Hypernatremia (mEq/L)	<146	146-150	151-157	158-165	>165
Hypokalemia (mEq/L)	>3.4	3.0-3.4	2.5-2.9	2.0-2.4	<2.0
Hyperkalemia (mEq/L)	<5.6	5.6-6.0	6.1-6.5	6.6-7.0	>7.0
Hypoglycemia (mg/dL)	≥65	55-64	40-54	30-39	<30
Hyperglycemia (mg/dL) (nonfasting and regardless of prior history of diabetes)*	<116	116-160	161-250	251-500	>500
Hypocalcemia (mg/dL) (corrected for albumin)	>8.4	7.8-8.4	7.0-7.7	6.1-6.9	<6.1
Hypercalcemia (mg/dL)	≤10.5	10.6-11.5	11.6-12.5	12.6-13.5	>13.5
Hypomagnesemia (mEq/L)	>1.4	1.2-1.4	0.9-1.1	0.6-0.8	<0.6
Hypophosphatemia (mg/dL)	≥2.5	2.0-2.4	1.5-1.9	1.0-1.4	<1.0
Hyperbilirubinemia (total bilirubin)	<1.1×ULN	1.1-1.5×ULN	1.6-2.5×ULN	2.6-5.0×ULN	>5.0×ULN
BUN	<1.25×ULN	1.25-2.5×ULN	2.6-5.0×ULN	5.1-10.0×ULN	>10.0×ULN
Hyperuricemia (uric acid) (mg/dL)	<7.5	7.5-10.0	10.1-12.0	12.1-15.0	>15.0
Creatinine	<1.1×ULN	1.1-1.5×ULN	1.6-3.0×ULN	3.1-6.0×ULN	>6.0×ULN

Key: BUN = Blood Urea Nitrogen; ULN = Upper Limit of Normal.

* The DMID toxicity table reports hyperglycemia detected in nonfasting specimens obtained from patients with no prior diabetes.

Enzymes					
	Grade 0	Grade 1	Grade 2	Grade 3	Grade 4
AST (SGOT)	<1.25×ULN	1.25-2.5×ULN	2.6-5×ULN	5.1-10×ULN	>10×ULN
ALT (SGPT)	<1.25×ULN	1.25-2.5×ULN	2.6-5×ULN	5.1-10×ULN	>10×ULN
GGT	<1.25×ULN	1.25-2.5×ULN	2.6-5×ULN	5.1-10×ULN	>10×ULN
Alkaline Phosphatase	<1.25×ULN	1.25-2.5×ULN	2.6-5×ULN	5.1-10×ULN	>10×ULN
Amylase	<1.1×ULN	1.1-1.5×ULN	1.6-2.0×ULN	2.1-5.0×ULN	>5.1×ULN
Lipase	<1.1×ULN	1.1-1.5×ULN	1.6-2.0×ULN	2.1-5.0×ULN	>5.1×ULN

Key: ALT (SGPT) = Alanine Aminotransferase (Serum Glutamic Pyruvic Transaminase); AST (SGOT) = Aspartate Aminotransferase (Serum Glutamic Oxaloacetic Transaminase); GGT = Gamma-Glutamyl Transferase; ULN = Upper Limit of Normal.

COAGULATION					
	Grade 0	Grade 1	Grade 2	Grade 3	Grade 4
Fibrinogen (mg/dL)	>200 - <400	100-200 (low) or 400-600 (high)	50 - <100 (low) or >600 (high)	<50 (low)	Fibrinogen associated with gross bleeding or with disseminated coagulation
Activated Partial Thromboplastin (APPT)	<1.01×ULN	1.01-1.66×ULN	1.67-2.33×ULN	2.34-3×ULN	>3×ULN
Prothrombin Time (PT)/International Normalized Ratio (INR)	<1.01×ULN	1.01-1.25×ULN	1.26-1.5×ULN	1.51-3.0×ULN	>3×ULN

Key: ULN = Upper Limit of Normal.

Number and percentage of subjects with at least a 2-grade increase from baseline or a post-baseline grade 4 abnormality (based on DMID criteria) will be summarized by treatment arm. Percentages for each lab test will be based on the number of subjects with a post-baseline evaluation of that laboratory test. A table will be provided which gives all laboratory results for a given laboratory test for subjects who have at least one 2-grade increase from baseline or a post-baseline grade 4 abnormality.

The number and percentage (based on the number of subjects with a normal level at baseline) of subjects in each treatment group with an elevated transaminase level ($>3 \times \text{ULN}$, $>5 \times \text{ULN}$, and $>10 \times \text{ULN}$), an elevated bilirubin level ($>1.5 \times \text{ULN}$ and $>2 \times \text{ULN}$) will be presented by study visit. A table of subjects who meet the laboratory criteria for Hy's law will also be provided. The laboratory criteria for Hy's law is defined as ALT or AST $>3 \times \text{ULN}$, ALP $\leq 2.0 \times \text{ULN}$, and total bilirubin $>2 \times \text{ULN}$.

Detailed patient listings of all laboratory data collected during the study will be provided. Laboratory values outside normal limits will be identified in the patient data listings with flags for low (L) and high (H) as will laboratory values that meet the clinically notable (CN) thresholds.

